5.3 Subject Enrollment

Before subjects begin participation in any study-specific activities/procedures, Amgen requires a copy of the site's written institutional review board/independent ethics committee (IRB/IEC) approval of the protocol, informed consent form, and all other subject information and/or recruitment material, if applicable (see Section 11.3).

The subject or their legally authorized representative must personally sign and date the IRB/IEC and Amgen approved informed consent before commencement of study-specific procedures.

A subject is considered enrolled when the investigator decides that the subject has met all eligibility criteria and has received the enrollment confirmation from sponsor. The investigator, designee, or staff member is to document this decision and date in the subject's medical record and in/on the enrollment case report form (CRF). Following enrollment, study treatment should begin as soon as possible but no later than 7 days after enrollment.

Each subject who enters into the screening period for the study (defined as the point at which the subject signs the informed consent) receives a unique subject identification number before any study-related activities/procedures are performed. The subject identification number will be assigned via interactive response technology (IRT). This number will be used to identify the subject throughout the clinical study and must be used on all study documentation related to that subject.

The subject identification number must remain constant throughout the entire clinical study; it must not be changed after initial assignment, including if a subject is rescreened.

5.4 Screen Failures

Screen failures are defined as subjects who consent to participate in the clinical study but are not subsequently enrolled in the study. A minimal set of screen failure information will be collected that includes demography, screen failure details, eligibility criteria, and any serious adverse events.

Individuals who do not meet the criteria for participation in this study (screen failure) may be rescreened once. Refer to Section [8.1.1](#).

6. Treatments

Study treatment is defined as any investigational product(s), non-investigational product(s), placebo, or medical device(s) intended to be administered to a study subject according to the study protocol.

Note that in several countries, investigational product and non-investigational product are referred to as investigational medicinal product and non-investigational medicinal product, respectively.

The Investigational Product Instruction Manual (IPIM), a document external to this protocol, contains detailed information regarding the storage, preparation, destruction, and administration of each treatment shown in [Table 6-1](#) below.

- 6.1 Treatment(s) Administered**
- 6.1.1 Investigational Products**

Table 6-1. Study Treatments

Amgen Investigational Product: ^a	
Study Treatment Name	AMG 160
Dosage Formulation	[REDACTED]
Unit Dose Strength(s)/ Dosage Level(s) and Dosage Frequency	
Part 1
 
The starting target dose of AMG 160 will be 1 dose level below the RP2D or otherwise the highest dose level deemed safe and tolerable as determined in the phase 1 monotherapy study (20180101). AMG 160 will be administered every 2 weeks after target dose is reached. [REDACTED]
 
[REDACTED]

Route of Administration	
Part 2
 
This is a dose expansion study. AMG 160 will be administered intravenously every 2 weeks 28-day cycle. The starting dose of AMG 160 will be the dose level that has been recommended as safe and tolerable in Part 1 of this study. To mitigate CRS, the cycle 1 dosing schedule may also be adapted the same way as Part 1 of this study.
 
Short-term IV infusion (approximately 60 minutes).
 
[REDACTED]

Amgen Investigational Product: ^a	
Study Treatment Name	AMG 160
Accountability	The planned dose, dose received, start date/time, stop date/time, and lot number of investigational product are to be recorded on each subject's eCRF(s).
Dosing Instructions	AMG 160 will be delivered using infusion pumps approved for use by the appropriate regulatory authority for the country in which the subject is undergoing treatment. [REDACTED] See pharmacy file for more detailed information regarding the storage, preparation, destruction, and administration of AMG 160.
Hospitalization Guidance	All subjects will be hospitalized for intensive monitoring for at least 48 hours post AMG 160 infusion during cycle 1 [REDACTED]. The subjects may be discharged after the 48-hour period if there are no clinically significant symptoms of CRS or other acute toxicities. Minimum hospitalization times for subjects will be as follows: 
• cycle 1: 48 hours after each infusion [REDACTED]• cycle 2:
– 24 hours after first infusion (48 hours in case a subject experienced grade ≥ 2 CRS or infusion reaction in cycle 1 (see Section 11.10.1 for grading of CRS)– 24 hours after each subsequent infusion• for cycles 1 and 2: study sites must have immediate access to a medical intensive care unit staffed by critical care providers• cycles 3 and 4: subject should be monitored in hospital or outpatient clinic for at least 4 hours after start of each infusion• cycle 5 and subsequent cycles: hospitalization not required unless a subject experiences an adverse event requiring hospitalization as described in Table 6-3, or if clinically indicated• re-start of treatment after an interruption due to adverse event: 8 hours Hospitalization beyond these recommended timelines based on adverse events may be allowed per investigator discretion.

C1D1 = cycle 1 day 1; CRS = cytokine release syndrome; DLRT = Dose Level Review Team; eCRF = electronic case report form; IPIM = Investigational Product Instruction Manual; IV = intravenous; IVSS = intravenous solution stabilizer; MTD = maximum tolerated dose; PK = pharmacokinetic(s); RP2D = recommended phase 2 dose; WFI = water for injection.

^a AMG 160 will be manufactured and packaged by Amgen and distributed using Amgen clinical study drug distribution procedures.

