6.2.2.1.2 Infusion Interruptions/Delays/Withholding and Re-start due to Adverse Events

6.2.2.1.2.1 General Guidelines

Subjects should be assessed for toxicity before each infusion of AMG 160. The severity of the toxicity will be graded using the CTCAE version 5.0, with the exception of CRS, which must be graded using the criteria referenced in the publication by Lee et al, 2014; TLS, which must be graded according to the Cairo Bishop criteria referenced in the publication by Coiffier et al, 2008; and immune-effector cell associated neurologic syndrome (ICANS) will be using the criteria referenced in the publication by Lee et al, 2019. Infusion modification and dose reduction due to a toxicity will be performed according to the instructions described below and outlined in [Table 6-3](#).

6.2.2.1.2.2 Infusion Interruptions due to Adverse Events

Events occurring during the infusion and requiring treatment interruption will be managed by immediate infusion interruption. The site should record any unscheduled interruption of an infusion on the eCRF and provide the start and stop date/time of the infusion.

Events requiring an infusion interruption are listed in [Table 6-3](#).

6.2.2.1.2.3 Delay of Subsequent Infusion due to Adverse Events

Events occurring after the end of the infusion and requiring a delay of treatment will be managed by delay of the subsequent infusion. The site should record any delay of an infusion on the eCRF and provide the start and stop date/time of the infusion.

Events requiring a delay of the subsequent infusion are listed in [Table 6-3](#).

Infusion interruptions or delays for other reasons need to be discussed with the Amgen medical monitor.

6.2.2.1.2.4 Re-start of Infusion

Re-starting treatment after an interruption/delay due to an adverse event or if the interruption/ delay was > 72 hours, regardless of the reason, should be performed under medical supervision. [REDACTED]

[REDACTED]. The following assessments should be performed as for days 1, 2, and 3 per the Schedule of Activities for cycle 1 (see Section [1.3](#)).

- vital signs, pulse oximetry
- physical examination
- neurological examination (only in case the treatment interruption was due to a neurologic event)
- weight
- ECOG
- safety labs (hematology, chemistry, coagulation, urinalysis)

The subject should be hospitalized for at least 48 hours after re-start of the infusion.

6.2.2.1.2.5 Dose Adjustments and Re-start at a Lower Dose Level

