For adverse events for which restart of treatment is allowed according to the guidelines outlined in [Table 6-3](#), treatment may be resumed at the same or lower dose.

Re-start at a lower dose level:

In the following cases, the next infusion administered should be at the previous (lower) dose level:

If the event occurred during the infusion and caused an interruption of the infusion for more than 72 hours and therefore the affected dose was withheld, or

If the event started after the end of an infusion and administration of the next infusion had to be delayed for more than 72 hours due to the event.

For specific events as outlined in [Table 6-3](#).

[figure not shown]

In either case, re-escalation to the target dose can be considered for the next infusion if treatment at the lower dose has been well tolerated with no events requiring dose interruption or delay as described in [Table 6-3](#). After the dose re-escalation, the following assessments should be performed as for day 8 through day 11 per the Schedule of Activities for cycle 1 (see Section [1.3](#)).

- vital signs, pulse oximetry
- physical examination
- neurological examination (only in case the treatment interruption was due to a neurologic event)
- safety labs (hematology, chemistry, coagulation, urinalysis)

The subject should be hospitalized for at least 48 hours after re-escalation.

In case an additional dose de-escalation is required, permanently discontinue treatment.

Table 6-3. Infusion Interruptions/Delays/Withholding/Permanent Discontinuation and Management of Adverse Events Including Dose Reductions

Grade	Description of Severity	Interruption/Delay	Specific Management	Re-start guidance	Permanent Discontinuation
Infusion-related Reaction					
1	Mild transient reaction; infusion interruption not indicated; intervention not indicated	N/A	Consider medication to control infusion reaction as deemed appropriate by the investigator according to local standard of care and institutional guidelines.	N/A	N/A

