2	Therapy or infusion interruption indicated but responds promptly to symptomatic treatment (eg, antihistamines, NSAIDs, narcotics, IV fluids); prophylactic medications indicated for ≤ 24 hours	Short-term infusion: Immediate interruption/delay until event has improved to grade ≤ 1 	Increase monitoring of vital signs as medically indicated until the subject is deemed medically stable	
 • Re-start possible, if successfully managed and improvement to ≤ grade 1 in ≤ 14 days. For short-term (approximately 60 minute) infusions, in case of infusion interruption, continue treatment with next scheduled infusion (do not resume prior infusion) 
 • Delay of the next infusion: 
 – < 7 days: administer the delayed infusion (as long as the next scheduled infusion is > 6 days from delayed infusion) and follow the schedule of assessments for the cycle day on which the infusion was originally planned. – > 7 days: skip the delayed infusion and resume schedule of assessments for the next scheduled infusion • Hospitalization: 48 hours • Dose modification: resume at the same dose or reduce to next lower dose, if clinically indicated • Additional measures:  and additional assessments as indicated in Section 6.2.2.1.2.4 	If subject missed more than 2 consecutive doses of AMG 160

Abbreviations and footnotes defined on last page of table.

Table 6-3. Infusion Interruptions/Delays/Withholding/Permanent Discontinuation and Management of Adverse Events Including Dose Reductions

Grade	Description of Severity	Interruption/Delay	Specific Management	Re-start guidance	Permanent Discontinuation
Infusion-related Reaction (continued)					
3	Prolonged (eg, not rapidly responsive to symptomatic medication and/or brief interruption of infusion); recurrence of symptoms following initial improvement; hospitalization indicated for clinical sequelae	Immediate interruption/ delay until event has improved to grade \leq 1	Consider supportive therapy including steroids as clinically indicated. Increase monitoring of vital signs as medically indicated until the subject is deemed medically stable.	
 As for grade 2 infusion-related reaction, with the exception of mandatory dose modification: reduce to next lower dose 	If subject missed more than 2 consecutive doses of AMG 160

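### Table 6-1 sets an 8-hour minimum hospital stay at re-start after an adverse-event interruption; Section 6.2.2.1.2.4 and Table 6-3 set 48 hours

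*Protocol*

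**What the plan says.** Table 6-1 (Section 6.1.1, hospitalization guidance) presents a list of minimum stays. The relevant entries are:

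- Cycle 1: "cycle 1: 48 hours after each infusion".
- Cycle 2: 24 hours after the first infusion, or 48 if the patient had CRS or an infusion reaction of grade 2 or higher in cycle 1; then "24 hours after each subsequent infusion".
- Cycles 3 and 4: 4 hours of monitoring, in hospital or in an outpatient clinic.
- Cycle 5 onward: "cycle 5 and subsequent cycles: hospitalization not required unless a subject experiences an adverse event requiring hospitalization as described in Table 6-3"; clinical need is a further ground for admission.
- Re-start: "re-start of treatment after an interruption due to adverse event: 8 hours".

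The closing sentence of that guidance allows longer stays at the investigator's discretion.

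Section 6.2.2.1.2.4 covers re-start after an interruption or delay caused by an adverse event, and any interruption or delay above 72 hours whatever its cause. It says: "The subject should be hospitalized for at least 48 hours after re-start of the infusion". Section 6.2.2.1.2.5 adds, for a return to the target dose, "The subject should be hospitalized for at least 48 hours after re-escalation".

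The re-start column of Table 6-3 repeats "Hospitalization: 48 hours" across the toxicity categories. For a grade 3 infusion reaction it reads "As for grade 2 infusion-related reaction, with the exception of mandatory dose modification: reduce to next lower dose", so the 48-hour stay for grade 2 carries over.

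**The concern.** One trigger, re-start after an adverse-event interruption, carries two stated minimums, and neither text gives way to the other. The wording of Table 6-1 makes anything beyond its figures optional, so it does not lead a reader back to 48 hours.

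The hospitalization rows of the Schedule of Activities point to Table 6-1 and do not mention Section 6.2.2.1.2.4. Table 1-4, which covers cycle 2 and beyond, is one of them, and those are the cycles where the figures diverge. From cycle 5, Table 6-1 also disagrees with itself: one bullet defers to Table 6-3 for adverse events needing admission, and the next says 8 hours.

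The stake is clinical. CRS is the identified risk in Table 2-1, and Section 11.10.1 describes raised risk over the first few days after dosing and says the syndrome can be fatal. Re-start applies to patients who have just had a toxicity. If CRS or a neurologic event recurred between 8 and 48 hours after re-start, it could begin outside hospital.

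The result is also odd. Section 6.2.2.1.1 sends a purely logistical delay above 72 hours to the adverse-event re-start instructions. From cycle 3, a patient delayed by a pump fault would stay 48 hours, while Table 6-1 would let a patient re-starting after CRS leave at 8.

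**Working it through.** No design calculation is involved. The check sets the texts side by side and takes differences.

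**Step 1: count the Table 6-3 re-start entries that state a stay.**

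| Table 6-3 entry | Stay stated |
|---|---|
| Infusion reaction, grade 2 | 48 h |
| CRS, grade 2 | 48 h |
| CRS, grade 3 | 48 h |
| Tumor lysis syndrome, grade 2 | 48 h |
| Neurological, grade 2 or higher | 48 h |
| Gastrointestinal, grade 2 | 48 h |
| Gastrointestinal, grade 3 or higher | 48 h |
| Other AMG 160-related, grade 3 or higher | 48 h |
| Not AMG 160-related, grade 4 | 48 h |

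That is nine of nine at 48 hours, plus the grade 3 infusion reaction by reference. The SARS-CoV-2 entries only ask the site to consider admission. One block of the table is redacted; the conflict does not depend on it.

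**Step 2: find the effective Table 6-1 minimum at re-start in each cycle.** A re-start infusion falls in some cycle, so the routine minimum for that cycle may exceed 8 hours. I give Table 6-1 the benefit of its longest applicable figure:

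effective minimum = max(routine minimum, 8 h); shortfall = 48 h − effective minimum.

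| Cycle | Routine minimum | Effective minimum | Shortfall |
|---|---|---|---|
| 1 | 48 h | max(48, 8) = 48 h | 0 h |
| 2, first infusion, after grade 2 or higher CRS or infusion reaction in cycle 1 | 48 h | max(48, 8) = 48 h | 0 h |
| 2, otherwise | 24 h | max(24, 8) = 24 h | 48 − 24 = 24 h (2-fold) |
| 3 and 4 | 4 h | max(4, 8) = 8 h | 48 − 8 = 40 h (6-fold) |
| 5 onward | none fixed | 8 h | 48 − 8 = 40 h (6-fold) |

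The re-start bullet does not say when its 8 hours begin. I assume the same starting point as the 48 hours.

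**Step 3: look for a precedence rule.** Section 6.2.2.1 sends sites to Table 6-3 for interruptions and delays, while the Schedule of Activities sends them to Table 6-1 for hospitalization. The two routes give different answers, and no text ranks them.

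**Step 4: apply the correction.** With the re-start bullet at 48 hours, max(routine, 48) = 48 in every cycle and the shortfall is 0 throughout.

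**The case against.** The strongest counter-argument is about scope. The protocol distinguishes an interruption (event during the infusion) from a delay (event after it). The Table 6-1 bullet names only an interruption, and infusions last about 60 minutes, so many re-starts would follow delays that the 8-hour figure arguably does not reach. This does not succeed. Section 6.2.2.1.1 refers to the re-start instructions as those for adverse-event interruptions even when it applies them to delays. On the narrow reading, Table 6-1 would leave delayed patients with only its routine minimum, which is 4 hours in cycles 3 and 4, a gap of 48 − 4 = 44 hours.

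Several other points have weight:

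- A 48-hour stay satisfies every text, so a cautious site breaches nothing. Taking the longest minimum across the whole protocol gives 48 hours and no shortfall. The protocol states no such rule.
- Section 6.2.2.1 asks for consultation with the medical monitor, and the re-start entries for CRS grades 2 and 3 and tumor lysis syndrome grade 2 repeat this. It is a real safeguard against acting on Table 6-1 alone.
- The day 1 to 3 assessments still apply after re-start, and the documents give no timing for recurrence, so harm is possible rather than shown.
- From cycle 5 the pointer to Table 6-3 softens the conflict.
- The 8 may be a slip for 48.

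These points lower the risk. They do not reconcile the two minimums, and a probable slip is a reason to correct the figure.

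**Conclusion.** The inconsistency is real and should be fixed. Table 6-1 stands alone at 8 hours against Section 6.2.2.1.2.4 and every Table 6-3 entry that states a stay. The conflict bites fully from cycle 3 (40 hours short) and partly in cycle 2 (usually 24 hours short); it has no effect in cycle 1. These sizes assume that a site applies the longest minimum within Table 6-1 and does not consult the re-start section.

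The conclusion is confined to patient safety. Adverse events are collected through safety follow-up whatever the length of stay (Section 8.2.4.1.1), so no effect is claimed on dose-limiting toxicity counts, the primary endpoint or the stopping rules.

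**What to change.** Change the Table 6-1 re-start bullet to: *at least 48 hours (see Section 6.2.2.1.2.4 and Table 6-3)*. This adds no new conflict with the SARS-CoV-2 entries: Section 6.2.2.1.2.4 already applies 48 hours to any delay above 72 hours, and the bullet would cross-refer to Table 6-3.

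In the same edit, a minor alignment is worthwhile. For cycles 3 and 4, Table 6-1 counts the 4 hours of monitoring from the start of the infusion, while Table 1-4 counts them after it. Use the Table 1-4 wording, which gives the longer period.

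The cost is one bullet and one phrase. There is no statistical cost, and admissions lengthen only at sites that would have used the 8-hour figure.

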6.1.1.1 Non-Amgen Investigational Imaging Products

⁶⁸Ga-PSMA-11 is a non-Amgen investigational product administered as part of PET/CT imaging assessments in this study.

6.1.2 Non-investigational Products

No non-investigational products will be used in this study.

[figure not shown]
6.1.3 Medical Devices

Other non-investigational medical devices may be used in the conduct of this study as part of standard care.

Non-investigational medical devices (eg, syringes, sterile needles), that are commercially available are not usually provided or reimbursed by Amgen (except, for example, if required by local regulation). The investigator will be responsible for obtaining supplies of these devices.

6.1.4 Other Protocol-required Therapies

All other protocol-required therapies, including glucocorticoids and tocilizumab/siltuximab, that are commercially available are not provided or reimbursed by Amgen (except if required by local regulation). The investigator will be responsible for obtaining supplies of these protocol-required therapies.

For administration of [REDACTED] or tocilizumab/siltuximab after occurrence of CRS, follow guidance in [Table 6-3](#). Tocilizumab should be administered according to warning and precautions guidelines for tuberculosis provided in the tocilizumab regional prescribing information. [REDACTED]

Sites are required to have tocilizumab or siltuximab (if tocilizumab not available) on site for potential treatment of CRS. See Section [9.4.1.1.1](#) for siltuximab stopping rules.

6.1.5 Other Treatment Procedures

Sites are required to have tocilizumab or siltuximab (if tocilizumab not available) on site for potential treatment of CRS.

6.1.6 Product Complaints

A product complaint is any written, electronic or oral communication that alleges deficiencies related to the identity, quality, durability, reliability, safety, effectiveness, or performance of a drug, combination product, or device after it is released for distribution to market or clinic by either (1) Amgen or (2) distributors and partners for whom Amgen manufactures the material. This includes all components distributed with the drug, such as packaging drug containers, delivery systems, labeling, and inserts.

This includes any investigational/non-investigational product(s) provisioned and/or repackaged/modified by Amgen (ie, AMG 160).

Any product complaint(s) associated with an investigational or non-investigational product supplied by Amgen are to be reported according to the instructions provided in the IPIM.

6.1.7 Excluded Treatments, Medical Devices, and/or Procedures During Study Period

The following treatments and/or procedures are excluded during the treatment period of the study (unless approved by Amgen medical monitor):

- any anticancer therapy other than AMG 160, such as:
 - cytotoxic and/or cytostatic drugs
 - radiation therapy (with the exception of radiotherapy for symptom control, such as bone or brain metastases after discussion with the medical monitor). The radiation therapy should not include the thoracic field and must have been completed at least 7 days before the subsequent dose of AMG 160.

- immunotherapy
- chronic systemic corticosteroid therapy ([REDACTED]) or any other immunosuppressive therapies (except for the management of acute, treatment-related toxicities such as transient [ie, for up to 2 weeks] use of corticosteroids and tocilizumab)
 - high-dose corticosteroid therapy ([REDACTED]) is only allowed for up to 7 days
- any other investigational agent with the exception of ⁶⁸Ga-PSMA-11 (if applicable)
- any major surgery (exceptions can be discussed with the medical monitor and may be permissible)

